#### 5.2.3 DETAILS OF MR IMAGING

**Dynamic contrast-enhanced MR imaging**: All imaging should be performed on a high field (1.5T or 1T) system with a dedicated bilateral breast surface coil for signal reception. Multiple thin slice (in plane resolution 1.3 x 1.3 mm; slice thickness 4 mm) MR sequences (temporal resolution 45 seconds) should be acquired coronally through both breasts out to 450 seconds, the first two data sets obtained prior to, and the remainder following, intravenous bolus injection of contrast agent (0.1 mmol Gd-DTPA/ kg body weight). High resolution (0.7 mm x 0.9 mm in plane) post-contrast, fat-suppressed 3D MR images (allowing maximum intensity projection or multi-planar reformatting) should be obtained coronally for morphological information and further sagittal images acquired if chest wall invasion is suspected. DCE-MRI at 12 months should be performed as detailed above. Data analysis will include:

- i) **Evaluation of the behaviour of the signal intensity time curve** should be carried out from the most rapid and strongly enhancing region-of-interest from within any given lesion, taking care to exclude adjacent blood vessels. These areas should be identified semi-automatically by means of parametric images generated by Advantage Windows or equivalent workstations, which selectively mark and allow pixel-by-pixel interrogation of signal intensity change over time on the anatomical images. Lesions should be classified according to morphological appearance and the pattern of the time signal intensity curve as detailed previously (Kaiser and Zeitler, 1989; Fischer et al, 1993; Kuhl et al, 1999). Type I lesions should be considered benign/ normal (score 0); type II indeterminate (score 1); type 3 suspicious/ malignant (score 2).
- ii) **Morphological criteria of malignancy** will include: ill-defined, irregular or spiculated borders, or peripheral or non-uniform enhancement on high-resolution images. Lesions should be classified as benign/ normal (score 0), indeterminate (score 1) or suspicious/ malignant (score 2).
- iii) **Scoring system**: A combined score (time signal intensity curve pattern and morphological information) of 2 or more should be considered suspicious of malignancy, 1 an equivocal

result, and a score of 0 will equal a normal/ benign result. Each lesion demonstrated should be considered independently.

#### 5.2.4 CHANGE IN SURGICAL MANAGEMENT

Changes in surgical management should be obtained by comparing the documented treatment option recorded on a study-specific proforma before randomisation, with those completed after MR imaging.

#### 5.2.5 MR DATA TRANSFER

To facilitate transfer of MR information, the location and extent of tumour tissue should be drawn and separately identified on images of the breast obtained in each orthogonal plane from reformatted images, with reference to the entire breast. The maximum diameter in each plane, the proximity to skin/ chest wall/ nipple retro-areolar complex should be marked on hard copy and sent to both breast surgeon and pathologist. A reference copy should be retained at the MR centre.

### 6. RANDOMISATION

This is a multi-centre, hospital-based study involving multidisciplinary groups using high field (1T or 1.5T) MR systems (GE, Phillips and Siemens) with dedicated breast coils, fast scanning capabilities and post- processing facilities.

#### 6.1 **RECRUITMENT PROCESS**

Invitation to participate will be made at the time at which treatment options are discussed and agreed. Whilst at the out-patient clinic, women scheduled for wide local excision will be invited to participate in the study by the Consultant Breast Surgeon or the Consultant Radiologist, but will subsequently receive further information, including the Patient Information Leaflet, from the study research nurse. The research nurse will then contact patients, by telephone, the following working day. If the patient wishes to participate the research nurse will arrange an early (within the next 1-2 working days) and mutually convenient meeting to obtain written consent. Randomisation of consenting patients will be by telephone to the central trials office (the CTRU), using an automated 24-hour telephone randomisation system.

#### 6.2 **RANDOMISATION**

Randomisation will be administered by telephone by the CTRU, using an automated 24-hour telephone randomisation system. Informed written consent for entry into the study will be obtained prior to randomisation. If the patient is randomised to receive an MRI scan, the scan should be booked and the patient informed of the scan date as soon as possible.

The following information will be required at randomisation:

- basic patient details including name and date of birth
- name of consultant breast surgeon
- confirmation that X-ray mammography and ultrasound have been performed
- mammographic breast density score (1 to 4) evaluated according to the Breast Imaging Reporting and Data System (BIRADS)
- confirmation of eligibility and written informed consent.

# Direct line for 24-hour randomisation [name]

Once eligibility has been confirmed and the necessary details obtained, patients will be randomised to receive **MR imaging** or **no further investigations** on a 1:1 basis, and will be allocated a trial number. Patient allocation will use a minimisation algorithm, which will employ the following stratification factors:

#### - Consultant breast surgeon

- Patient's age subdivided in to
  - < 50
  - $\geq$  50 years of age
- Breast density\*
  - a) BIRADS Group 1 (pattern 1 only)
  - b) BIRADS Group 2 (pattern 2, 3 and 4).

\*Homogeneously or heterogeneously structured dense fibroglandular tissue in a large percentage of the entire breast volume is the only mammographic or ultrasound finding to date which has helped define a subgroup of patients with multi-focal or multi-centric disease detected by MR imaging alone (Fischer et al, 1999; Berg and Gilbreath, 2000). Mammograms will be evaluated according to the Breast Imaging Reporting and Data System (BIRADS) and patients divided in to two groups – Group 1 in which the breast is almost entirely fatty (pattern 1) and Group 2 encompassing those with scattered fibro-glandular densities that could obscure a lesion on mammography (pattern 2); those in whom the breast tissue is of heterogeneous density (pattern 3); and those with extremely dense breast tissue (pattern 4).

### 7. QUALITY OF LIFE AND ECONOMIC EVALUATION

#### 7.1 QUALITY OF LIFE ASSESSMENT

In order to evaluate the impact of the investigations and treatment on the quality of life (QOL) of the women involved in the trial, questionnaires will be completed by the patients.

The Functional Assessment of Cancer Therapy, Breast Cancer Version (FACT-B) will be used to evaluate the impact on physical well-being, social well-being, emotional well-being, functional well-being and breast cancer concerns. FACT-B comprises the FACT-General (Cella et al, 1993) and ten

specific items related to breast cancer (Brady et al, 1997). The questionnaire has been developed over a number of years and has been used in several major UK trials (Walker et al, 1999). Satisfactory reliability and validity have also been demonstrated (Cella et al, 1993; Brady et al, 1997). For the purpose of this study the question GE3 "I am losing hope in the fight against my illness" has been removed. This does not affect the scalar structure of the questionnaire.

Anxiety and depression will be assessed using the Hospital Anxiety and Depression Scale (HADS) (Zigmond and Snaith, 1983). The HADS is a widely used questionnaire which has been shown to be reliable and valid in the detection of clinically significant anxiety and depression in patients with cancer (Razavi et al, 1990; Hopwood et al, 1991; Ibbotson et al, 1994). In addition, HADS scores have been shown to be sensitive to the effects of breast screening and recall within the context of the NHS programme (Walker et al, 1994, Gilbert et al, 1998).

An ad hoc cancer-specific questionnaire using a 4-point Likert scale will be used to examine concerns about tumour recurrence. This questionnaire will be developed and piloted during the first three months of the project. It will address the extent to which patients consider that various aspects of their management have minimised the risk of tumour recurrence. In those undergoing MRI, the perceived impact of this investigation on recurrence and satisfaction with management will be evaluated. The questionnaire will use response formats, such as Likert Scales, that have been shown to have satisfactory reliability and validity in other contexts. It is envisaged that the questionnaire will contain approximately 10 items. During the piloting phase, test-retest reliability will be assessed, and internal consistency (e.g. Cronbach's alpha) will be computed in order to determine if the questionnaire has satisfactory scalar properties. If this is the case, total scores, as opposed to individual items, will be used in the between-group comparisons.

The EQ-5D will be used to measure self-reported utility (EuroQol group, 1990). The EQ-5D is a standardised non-disease-specific instrument which describes and values health-related quality of life and provides a single index value for a number of different health states. The EQ-5D will be used in the economic evaluation (see section 7.3).

#### 7.2 TIMING OF QUALITY OF LIFE ASSESSMENTS AND ADMINISTRATION OF QUESTIONNAIRES

Patients will be asked to complete questionnaires at the following time intervals:

-	HADS	pre-randomisation
		8 weeks post randomisation
		6 and 12 months post initial surgery.

- FACT-B pre-randomisation 8 weeks post randomisation 6 and 12 months post initial surgery.
- Ad hoc questionnaire (to examine concerns about tumour recurrence) 8 weeks post randomisation 6 and 12 months post initial surgery.

-

EQ-5D

pre-randomisation8 weeks post randomisation6 and 12 months post initial surgery.

The first set of questionnaires should be given to the patient after written informed consent has been given, and prior to randomisation. It is essential that the questionnaires are completed by the patient before they are informed of the randomisation allocation, to ensure that all patients complete the questionnaires without any knowledge of any further investigations or treatment changes. The completed questionnaires should be returned to the CTRU. In order to maximise compliance, all subsequent questionnaires will be sent to the patient's home address by the CTRU. The CTRU will endeavour to check the patient's current status with the relevant research nurse before sending questionnaires. Pre-paid envelopes will be provided for the return of questionnaires. Patients not responding within two weeks will be sent a reminder letter. Patients not returning two consecutive sets of questionnaires will not be sent any further questionnaires. A letter of thanks will be sent to patients who return a set of completed questionnaires.

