#### 7.3 ECONOMIC EVALUATION

As part of the quality of life questionnaires, a small number of questions will be asked for use in the economic evaluation. These will centre around a woman's time away from usual activities due to her breast cancer treatment, and use of community-based health services.

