#### 9.2.3 QUALITY OF LIFE AND PATIENT SATISFACTION

Quality of life as assessed by the FACT-B, and anxiety and depression as assessed by the HADS, at 8 weeks post randomisation and 6 and 12 months post surgery. Concerns about tumour recurrence post-operatively will be assessed by an ad-hoc questionnaire at 8 weeks post randomisation and 6 and 12 months following surgery.

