# **11.** ANALYSIS PLAN (OUTLINE)

Analysis of the study will be performed in two stages, firstly at completion of the initial follow-up following surgery, and secondly, once the five-year follow-up has been completed in all patients. The primary analysis will be on an intention-to-treat basis. All hypothesis tests will be 2-sided and

at the 5% level: p-values less than 0.05 will be considered to be statistically significant. Formal hypothesis testing will be restricted to the primary endpoints only.

Inference will be based on available data only. Sensitivity analysis will be carried out if there are missing data to test the robustness of the conclusions, the results of which will be fully reported.

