#### **11.2.3** QUALITY OF LIFE AND PATIENT SATISFACTION

The six sub-scales of FACT-B (physical well-being, social well-being, emotional well-being, functional well-being, relationship with doctor, breast cancer concerns) and two sub-scale scores for HADS (anxiety, depression) will be transformed to a percentage of the maximum score for each sub-scale. Point estimates and 95% confidence intervals will be reported for the percentage means for each of the sub-scale scores at 6 months. Regression models will be used to adjust for baseline scores and other important covariates. Missing data patterns will be examined carefully. Methods that account for informatively missing data will be used if necessary.

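### Ending questionnaires after two consecutive non-returns adds avoidable, possibly informative missing data at 12 months

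*Combined protocol and SAP*

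**What the plan says.** Protocol section 7.2 sets out four occasions: before randomisation, 8 weeks after randomisation, and 6 and 12 months after initial surgery. HADS, FACT-B and EQ-5D are due at all four, and the recurrence-concern questionnaire at the last three. The first set is handed over after consent; later sets are posted by the trials unit after a status check. The chasing rule is "Patients not responding within two weeks will be sent a reminder letter". The stopping rule is "Patients not returning two consecutive sets of questionnaires will not be sent any further questionnaires".

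Section 7.3 puts the patient-reported economic questions in the same sets: "These will centre around a woman's time away from usual activities due to her breast cancer treatment, and use of community-based health services".

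Section 9.2.3 lists FACT-B and HADS "at 8 weeks post randomisation and 6 and 12 months post surgery" as an endpoint. The analysis in section 11.2.3 names only one of these times: "Point estimates and 95% confidence intervals will be reported for the percentage means for each of the sub-scale scores at 6 months". On missing data the same section says "Missing data patterns will be examined carefully. Methods that account for informatively missing data will be used if necessary". Section 11 gives the general basis, "Inference will be based on available data only", followed by a commitment to a fully reported sensitivity analysis if data are missing. Section 11.1.2 adds an adjustment for differential follow-up in the within-trial cost-effectiveness analysis.

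**The concern.** The rule treats silence on two occasions as a reason to stop asking. With only four sets, two early misses turn what might have been intermittent non-response into permanent loss. The 12-month set is a listed quality-of-life time point. It is also the only set that coincides with the end of the first year, which is when section 11.1.2 says detailed resource-use data are gathered. The economic evaluation is listed as a primary endpoint (section 9.1.2) and takes a societal perspective, so productivity costs depend on time away from usual activities.

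The analysis is weakened too. Among women who missed the 8-week and 6-month sets, the chance of observing a 12-month value is zero by design. They have no post-randomisation questionnaire data at all. Weighting cannot represent that group, and imputation must borrow entirely from women with a different return history. Replies at 12 months from earlier non-responders would be the most direct evidence on whether such women differ, and the rule prevents that evidence from being collected. The rule also works against section 7.2's own aim of maximising compliance.

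**Working it through.** **The plan's own figure.** Section 10.1 gives 1840 women for 15% v 10%, 90% power, two-sided 5%, chi-squared test without continuity correction. Per arm:

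[1.960 × √(2 × 0.125 × 0.875) + 1.282 × √(0.15 × 0.85 + 0.10 × 0.90)]² / 0.05² → 918

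That is 1836 in total, and 920 per arm gives 90.1% power. The figure reproduces. It is used here only as the denominator; the plan states no questionnaire return rate and no quality-of-life sample size.

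**Which return histories the rule affects.**

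| Sets missed | Consequence |
|---|---|
| 8 weeks and 6 months | 12-month set never sent |
| Pre-randomisation and 8 weeks | 6- and 12-month sets never sent, but only if the first set counts, which the text does not say |
| 6 and 12 months | None; no set remains |
| One set, or two that are not adjacent | None |

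**What stops and what does not.** Stopped: FACT-B, HADS, the recurrence-concern questionnaire and EQ-5D (section 7.2), with time away from usual activities and community service use (section 7.3). Neither of those two cost items is named on any form in section 8; section 8.5 has an open entry for other health economics data, but it belongs to the surgical record. Not stopped: theatre time and surgical details (8.5), post-operative course and discharge (8.7), re-admissions and further surgery at 6 months, and chemotherapy, radiotherapy and adjuvant therapy at 12 months (8.8). Hospital notes are also reviewed after recurrence (11.1.2).

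**Size.** Let
- a = P(miss 8 weeks)
- b = P(miss 6 months, given 8 weeks missed)
- r = P(would return the 12-month set if sent, given both missed).

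Share not sent the 12-month set = a × b. Share lost because of the rule = a × b × r. All three probabilities are assumptions: a from 10% to 30%, b from independence (b = a) to 80%, r from 10% to 50%. The pre-randomisation set is taken not to count.

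| Case | a, b, r | Not sent | Lost because of the rule |
|---|---|---|---|
| Low | 0.10, 0.10, 0.10 | 0.010 × 1840 = 18 | 0.001 × 1840 = 2 (0.1%) |
| Mid | 0.20, 0.50, 0.30 | 0.100 × 1840 = 184 | 0.030 × 1840 = 55 (3.0%), about 28 per arm |
| High | 0.30, 0.80, 0.50 | 0.240 × 1840 = 442 | 0.120 × 1840 = 221 (12%) |

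**Possible bias.** If the women lost because of the rule differ from the rest by d SD, a 12-month arm mean shifts by roughly (share lost) × d. With d = 0.5 (assumed):
- mid case: 0.030 × 0.5 = 0.015 SD
- high case: 0.12 × 0.5 = 0.06 SD.

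These shares use all randomised women as denominator, which slightly understates the share among would-be responders. With 700 responders per arm, the mid case becomes 55 / (1400 + 55) = 3.8%, or 0.019 SD.

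The between-arm shift is smaller. If one arm loses 1.5 times the share of the other, it is 0.5 × 0.030 × 0.5 = 0.0075 SD in the mid case and 0.5 × 0.12 × 0.5 = 0.03 SD in the high case.

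For scale, the 95% CI half-width for a difference in means is 1.96 × √(2/920) = 0.091 SD, or 0.105 SD with 700 per arm.

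**The case against.** The best defence is that stopping after two ignored sets and their reminders limits the burden on women under cancer treatment, and that little is lost. Most of these women would not have answered a third set anyway (70% in the mid case). Quality of life is secondary and not formally tested, 12 months has no named analysis, and the plan already has a reminder, examination of missing-data patterns, methods for informative missingness if needed, a sensitivity analysis and an adjustment for differential follow-up.

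Much of this stands, and it rules out several stronger readings.

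- *The rule makes the missingness informative.* It does not. It acts on recorded return history; any informativeness comes from why the first two sets were not returned. The rule adds missing data to whatever mechanism is present.
- *The women lost are those most affected by treatment, so the arms are biased.* The trial is open and treatment burden may differ by arm, so this is possible. But nothing in the documents says who fails to reply; disengaged women who feel well are equally possible.
- *Cost collection, or the primary economic endpoint, is lost.* Only the questionnaire-based items stop. The key within-trial effect is recurrence, and EQ-5D mainly supplies utilities for the extrapolation model.
- *The 6-month analysis is lost.* That requires the pre-randomisation set to count. For any woman who returned it, the rule cannot remove her 6-month set.
- *The woman is withdrawn.* Only mailings stop; clinical follow-up runs to 5 years.

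What the defence does not answer is that none of these safeguards recovers a set never sent. The reminder works within a set. The missing-data provisions name no method or trigger, and the follow-up adjustment is not described as covering questionnaire non-return. Burden can be limited by letting women decline.

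**Conclusion.** The point holds in a limited form. For a woman who misses the 8-week and 6-month sets, the 12-month set is missing with certainty because of the trial's own rule. That is avoidable, and it may be informative. It affects the 12-month patient-reported outcomes, EQ-5D and the two questionnaire-based cost items. Hospital resource use and the sample size are untouched.

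The rule's added loss is roughly 0.1% to 12% of women, mid case 3.0%. The quality-of-life bias is probably small against the trial's precision. Both rest on assumed return rates and an assumed 0.5 SD difference; the direction is unknown, and no effect on costs has been quantified. The case for change rests on how easily the loss can be avoided and on the lack of another listed source for the two cost items, not on a demonstrated bias. This is a cheap improvement, not a flaw that threatens the trial's conclusions.

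**What to change.** In section 7.2, replace the stopping sentence with: *All scheduled questionnaire sets will be sent to every woman unless she has died or has asked not to receive them; non-return of earlier sets is not withdrawal.* Keep the status check before posting and the two-week reminder. Record declined separately from not returned, so that the analysis can tell the two apart. This also removes the ambiguity about whether the pre-randomisation set counts.

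The cost is a one-sentence amendment and one extra mailing (two if the pre-randomisation set currently counts), plus reminders, for a minority of women. In the mid case that is up to 184 extra 12-month sets for about 55 returned. There is a small risk of unwelcome post, limited by the opt-out.

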#### 7.3 ECONOMIC EVALUATION

As part of the quality of life questionnaires, a small number of questions will be asked for use in the economic evaluation. These will centre around a woman's time away from usual activities due to her breast cancer treatment, and use of community-based health services.

# 8. DATA COLLECTION

Data generated by all centres will be collected, monitored and computerised by the NYCTRU. All centres will be asked to complete a log of all patients who are approached to enter the trial including those who refuse randomisation. Data collection for randomised patients will include: initial clinical details pre-randomisation, surgical procedure performed, histopathology, postoperative information, hospital re-admission, and recurrence details as listed below. As some variations in ancillary management (e.g. radiotherapy) and pathological examination exist between centres, the current management policies of each centre will be recorded at baseline and adherence to these policies monitored.

Attempts have been made to reduce data collection to a minimum, with the majority of data being completed by the research nurse and much of the remainder being collected routinely within the framework of the NHS BSP.

